### 8.2. Key Definitions and Derivations

Treatment emergent adverse events (TEAEs) are defined as any adverse events that start or increase in intensity on or after the first dose of treatment on Day 1.

Timing-specific adverse events are defined as any adverse events that occur or increase in intensity during any specifically defined study milestones: open-label stabilization period (OLAE), double-blind R/WD phase (RWDAE), taper down (TDAE) and off study drug (ODAE).

Prior medications are defined as medications entered in the eCRF that either start, or end before the first dose of study medication. Concomitant medications are defined as medication on the eCRF that are taken on or after or are ongoing at the start date of dosing.

Duration of exposure (days) to study drug is defined as (Date of Last Dose – Date of First Dose) +1. If the date of last dose is unknown, then the date of last clinical visit will be used to impute the date of last dose.

Baseline is defined as the last measurement taken before the first dose of ecopipam in the open-label stabilization period.

Change from baseline will be calculated for the post-baseline assessments as post-baseline value – baseline value. Similarly, change from randomization will be calculated for the post-randomization assessments as post-randomization value – randomization value.

Demographics and baseline characteristics will be derived as follows:

Age at Study Day 1 = (Study day 1 visit date - date of birth + 1) / 365.25 and truncated to complete years.

Height (in cm) = height (in inches) \* 2.54

This document is confidential.

SAP text Version: SAP text 3.0 6-Dec-2023

Controlled Document ID: 3903A.02, Effective Date 31-Aug-2020

Weight (in kg) = weight (in lbs) \* 0.4536

BMI (kg/m2) = Weight(kg)/[Height(m)2]

To calculate weight, height and BMI z-scores for children and adolescents, Centers for Disease Control and Prevention (CDC) growth charts will be used (see section 13)

For adults, weight, height and BMI z-scores will be calculated as follows:

(Weight, Height and BMI) z-scores = (Weight, Height and BMI) - mean (Weight, Height and BMI) of all subjects at the baseline visit/ Standard deviation of (Weight, Height and BMI) of all subjects at the baseline visit.

Treatment compliance, as a percentage, will be derived on the eCRF as follows:

Treatment compliance (%) = Actual Tablets Used\*100/Expected Tablets Used

Actual Tablets Used is based on Tablets Dispensed minus (Tablets Lost or Discarded + Tablets Returned)

Expected Tablets Used is based on the Number of Days between visits and the Number of Tablets required to achieve assigned dosage based on the subject's baseline weight.

YGTSS scores will be derived without imputing missing values. The scores will be calculated only if all the questions are answered.

- Total Motor Tic Severity Score (range 0-25) = Motor Number + Frequency + Intensity + Complexity + Interference
- Total Vocal Tic Severity Score (range 0-25) = Vocal Number + Frequency + Intensity + Complexity
   + Interference
- Total Tic Severity Score (range 0-50) = Motor Tic Severity + Vocal Tic Severity
- Total Yale Global Tic Severity Scale Score (range 0-100) = (Total Tic Severity Score + Impairment)

### 8.3. Missing Data

Partial dates of medications will be imputed solely for the purpose of defining prior/concomitant status for medications. Dates will be defined using the hierarchy of derivations below.

- For missing start day where month and year are present, the start day will be set to the 1st of the
  month, unless the month and year are the same as the first dose month and year and the 1st of
  the month is before the first dose date, in which case, the start date will be set to the first dose date.
- For missing start day and month where year is present, the start day and month will be set to

January 1st, unless the year is the same as the first dose year and January 1st is before the first dose date, in which case, the start date will be set to the first dose date.

- For missing end day where month and year are present, the end day will be set to the last day of the month, unless the month and year are the same as the trial termination month and year, in which case, the end date will be set to the trial termination date.
- For missing end day and month, where year is present, the end date will be set to the trial termination date if the years are the same. If the trial termination year is greater than the end year, the end day and month will be set to December 31st.

Partial onset dates for adverse events will be imputed in the same manner described above for partial start dates for the purpose of defining treatment emergent status.

#### 8.4. Visit Windows

The following visit windows will be used in the summarization or analysis of data. If the subject's last non-missing data point falls within the window, even if additional data points fall within the window, then that last data point will be used. Else, if more than 1 data point falls within a window then the data point closest to the target day will be used. If there are 2 data points equidistant to the target day, one high and one low, then the high data point will be used. Visit windowing will not be applicable to follow-up visits. If a subject terminates the study early, all assessments collected at the Early Termination visit will be assigned to the next scheduled visit (per Schedule of Assessments for the parameter) where the assessment would have been collected.

If Baseline is Day 1, then:

Day 15 (target day = 15) 2 - 21 and no randomization

Week 4 (target day = 29) 22 - 42 and no randomization

Week 8 (target day = 57) 43 - 70 and no randomization

Week 12 (target day = 85) 71 and above with no randomization

Week 13 (target day = 92) 78 - 95 and randomized

Week 14 (target day = 99) 96 - 102 and randomized

Week 15 (target day = 106) 103 - 109 and randomized

Week 16 (target day = 113) 110 - 119 and randomized

Week 18 (target day = 127) 120 - 133 and randomized

Week 20 (target day = 141) 134 - 147 and randomized

Week 22 (target day = 155) 148 - 161 and randomized

Week 24 (target day = 169) 162 and above (randomized and not a follow-up visit)

# 8.5. Pooling of Centers

Analyses will not include study site as a factor in the model. Region (North America and Europe) will be included, so sites will not be pooled based on the number of subjects, but by region.

# 8.6. Subgroups

Subgroup analyses will be conducted on all efficacy endpoints, demographics, disposition and exposure for the following populations:

- Children (≥ 6 and < 12 years of age), Adolescents (≥ 12 and < 18 years of age), including Children and Adolescents combined (≥ 6 and < 18 years of age), and Adults (≥ 18 years of age)
- Region (North America and Europe)
- Males and Females
- Ethnicity

Additionally, Time from Randomization to a loss of ≥ 50% improvement on the YGTSS-TTS will also be analyzed using the following subgroups:

• Early Responders (at Week 4) and Later Responders (at Week 8)

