5.2.2. Clinical Data

Clinical Studies in Subjects with TD

With respect to TD, the following clinical studies support the use of ecopipam in patients with this disease:

Study PSY301

This was a Phase 2a, multicenter, non-randomized, open-label study of 44.8 mg ecopipam (50 mg ecopipam HCl) daily (Weeks 1–2) and then 89.6 mg (100 mg ecopipam HCl) daily (Weeks 3–8) in 18 adult subjects (\geq 18 to < 65 years of age) with TD. The primary efficacy end point was the change in the Yale Global Tic Severity Scale, Total Tic Score (YGTSS-TTS) from Baseline to Week 8.

Mean (SD) YGTSS-TTS was 30.6 (8.8) at Baseline and 25.3 (9.2) at 8 weeks (2-tailed paired t17 = 4.4; p = 0.0004). Mean (SD) YGTSS impairment score was 29.7 (10.9) at Baseline and 22.8 (13.7) at final visit (t17 = 2.2; p = 0.04).

There was no significant change in premonitory urges or psychiatric symptoms. Mean change in weight was -0.7 kg (p = 0.07). The most commonly reported adverse events were sedation (39%), fatigue (33%), insomnia (33%), somnolence (28%), anxiety (22%), headache (22%), and muscle twitching (22%).

Study PSY302

Study PSY301 was followed by a Phase 2, placebo-controlled, cross-over study of ecopipam in 40 children and adolescents with TD which further demonstrated that ecopipam treatment

Protocol EBS-101-TD-301 Version 9.0, 05 March 2024

decreases motor and phonic tics as assessed by the YGTSS-TTS in children and adolescents with TD. This study was a randomized, double-blind, placebo-controlled crossover study to evaluate the safety, tolerability, and efficacy of ecopipam in children and adolescents with TD. Forty pediatric patients (7-17 years of age) with TD and a total tic score of 20 on the YGTSS were randomized to ecopipam or placebo. The study consisted of an initial 30-day Treatment period (sequence 1), a 2-week Washout period, and a second 30-day Treatment period (sequence 2) where patients were crossed to the alternative treatment to which they were randomized.

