| | Abbreviation | Placebo (n=74) | Ecopipam (n=75) | P value | | | |
|---|---------------------------------|-------------------|-----------------|------------------------|--|--|--|
| Outcome M | Outcome Measures: mITT data set | | | | | | |
| Primary Outcome: Yale Global Tic Severity Scale-Total Tic Score (motor + phonic tic scales) Baseline to week 12 | YGTSS-TTS | -6.42 | -9.87 | 0.011 | | | |
| Key Secondary Outcome: Clinical Global Impression of Tourette Syndrome – Severity Baseline to 12 weeks | CGI-TS-S | -0.53 | -0.91 | 0.027 | | | |
| Predefined Hierarchy of Secondary Outcomes: | | | | | | | |
| Clinical Global Impression of Tourette Syndrome of Improvement Baseline to week 12 | CGI-TS-I | 3.42 | 3.04 | 0.079 | | | |
| Yale Global Tic Severity Scale -Global Severity score (motor + phonic + overall impairment scales) Baseline to week 12 | YGTSS- GS | -13.56 | -21.41 | 0.004 | | | |
| Caregiver Global Impression of Change At week 12 | CaGI-C | 3.55 | 2.49 | 0.007 | | | |
| Gilles de la Tourette Syndrome-Quality of Life Scale for Children and Adolescents Baseline to week 12 | C&A-GTS-QOL | -8.81 | -8.75 | 0.978 | | | |
| Subjects with a 25% improvement on the YGTSS-TTS At any time between baseline and 12 weeks | | 32 (43%) | 53 (76%) | OR 3.67 P <0.001 | | | |

The most frequent adverse events (≥ 5% and higher than placebo) were headache (15.8%), insomnia (9.2%), fatigue (7.9%), nasopharyngitis (6.6%), somnolence (7.9%), anxiety (5.3%), nausea (5.3%) and restlessness (5.3%). For less commonly reported adverse events, the same proportion of ecopipam- and placebo-treated patients reported suicidal ideation and depression. No deaths were reported in the study, 2 subjects treated with ecopipam and 1 subject treated with placebo experienced Serious AEs (SAEs), and 4 ecopipam-treated patients discontinued the study due to an adverse event. No metabolic events were observed and more patients on placebo gained weight than those who received ecopipam. No EPS-related events were observed and no difference from placebo was detected for other abnormal movement events. No clinically significant differences between ecopipam and placebo were noted in labs, vital signs, EKGs and in commonly used scales to detect anxiety, depression, suicidal ideation and behaviors, akathisia,

Protocol EBS-101-TD-301 Version 9.0, 05 March 2024

and tardive dyskinesia. Ecopipam did not adversely affect comorbid psychiatric conditions of ADHD.

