# 3.2. Secondary Objectives

The secondary objectives of this study are to evaluate the safety and tolerability of ecopipam dosed at 1.8 mg/kg/day (2 mg/kg/day ecopipam HCl) in children ( $\geq$  6 and < 12 years of age), adolescents ( $\geq$  12 and < 18 years of age), and adults ( $\geq$  18 years of age) with TD, to evaluate the maintenance of efficacy of ecopipam in adults ( $\geq$  18 years of age), and to characterize the pharmacokinetics (PK) of ecopipam in all subjects.

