**Total Number of Subjects:** 

Approximately 196 subjects (children and adolescents) will be enrolled into the open-label Stabilization Period in order to randomize 98 subjects age ≥ 6 to < 18 years of age assuming the stabilization Response rate in the open-label Stabilization Period is 50%. In addition, approximately 40 adult subjects are also expected to be enrolled.

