# 12.1. Adverse Events / Adverse Drug Reactions

An adverse event (AE) is any untoward medical condition that occurs in a patient while participating in this clinical study. Adverse events will be coded according to the Medical Dictionary for Regulatory Activities (MedDRA 25.0 or later) terminology and the severity of the toxicities will be graded according to the National Cancer Institute (NCI) Common Toxicity Criteria for Adverse Events (CTCAE), v4.03, where applicable. An adverse drug reaction (ADR) means any AE caused by a drug or biologic.

This document is confidential.

SAP text Version: SAP text 3.0 6-Dec-2023

Controlled Document ID: 3903A.02, Effective Date 31-Aug-2020

A Clinical Adjudication Committee (CAC) will review selected treatment emergent neurological adverse events that are known to occur as the result of dopamine receptor antagonists (see Appendix 16.5). The details of the CAC procedures and adjudication process will be reported in a CAC charter.

Treatment-Emergent Adverse Events (TEAEs) are those adverse events/adverse drug reactions that are recorded during or following the initiation of study treatment administration, and do not necessarily have a causal relationship to the use of the study medication. Treatment-Emergent Adverse Events (simply referred to as adverse events in summary tables) will be summarized.

The following adverse event summary tables will be summarized by treatment group:

- An overall summary with the number and percentage of patients reporting AEs, serious AEs
  (SAEs), maximum severity AEs, treatment-related AEs, treatment related SAEs, AEs leading to
  study treatment discontinuation and AEs with outcome of deaths.
- 2) AEs overall and by system organ class and preferred term.

In this summary, a patient is counted once at the system organ class and once at each preferred term within the system organ class.

- AEs overall and by system organ class, preferred term and initial daily dose level.
- 4) AEs overall and by system organ class, preferred term and region.
- 5) AEs overall and by system organ class, preferred term and weight band.
- 6) AEs overall and by system organ class, preferred term and time within the titration phase of open-label stabilization period. In all summaries by time the time windows are based on time since fist dose of ecopipam and will be as follows: 1-7, 8-14, 15-21, 22-28, 29-56, 57-84, 85-91, 92-98, 99-105, 106-112, 113-126, 127-140, 141-154, 155-168, 169-175, 176-184.

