- 7) AEs overall and by system organ class, preferred term and time within open-label stabilization period.
- 8) AEs overall and by system organ class, preferred term and time within the double-blind randomized withdrawal period.
- 9) AEs overall and by system organ class, preferred term and time within the safety follow up.
- 10) AEs overall and by system organ class, preferred term and maximum severity.

In this summary, a patient is counted once at the highest severity for which the event occurred in the system organ class and the highest severity for each unique preferred term within that system organ class. Therefore, patients may only contribute once to each preferred term and once to each system organ class.

11) Study-treatment-related AEs overall and by system organ class and preferred term.

All those AEs with relationship to treatment marked as "Possibly Related" or "Probably Related" or missing will be reported in the table.

- 12) Study-treatment related AEs by system organ class, preferred term and maximum severity
- 13) AEs leading to study treatment termination by system organ class and preferred term.
- 14) AEs leading to study treatment termination by system organ class, preferred term and maximum severity.
- 15) AEs by maximum severity, maximum relatedness and milestones (Up-titration, Open-label maintenance, double-blind R/WD (Weeks 13-16), double-blind R/WD (Weeks 17-24) and Down-titration).

A Serious Adverse Event (SAE) is an AE which falls into one or more of the following categories:

- Results in death.
- · It is immediately life-threatening.
- It requires in-subject hospitalization or prolongation of existing hospitalization.
- It results in persistent or significant disability or incapacity.
- Results in a congenital abnormality or birth defect.
- It is an important medical event that may jeopardize the subject or may require medical intervention to prevent one of the outcomes listed above.

Serious adverse events will be summarized by treatment group and combined over both treatment groups. A summary by age group (Children (≥ 6 and < 12 years of age), Adolescents (≥ 12 and < 18 years of age), and Adults (≥ 18 years of age)) will also be provided.

16) SAEs overall and by system organ class and preferred term.

In this summary, a patient is counted once at the system organ class and once at each preferred term within the system organ class.

- 17) Treatment related SAEs overall and by system organ class and preferred term.

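### Safety in children, adolescents and adults is a secondary objective, but no planned table gives the incidence of non-serious AEs or of AEs of special interest by age group

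*SAP*

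**What the plan says.** SAP 3.2 opens "The secondary objectives of this study are to evaluate the safety and tolerability of ecopipam" and then names children, adolescents and adults, each with an age range. Protocol 6.2 says the same.

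SAP 8.6 sets the scope of the subgroup work: "Subgroup analyses will be conducted on all efficacy endpoints, demographics, disposition and exposure for the following populations". The groups that follow include 6 to <12, 12 to <18, 6 to <18 combined, and 18 and over. Safety is not among the items to be split.

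SAP 12.1 lists the AE tables:
- Tables 1 to 15 cut AEs by initial daily dose, region, weight band, time, severity, relatedness and study milestone. Table 5, for example, is "AEs overall and by system organ class, preferred term and weight band". None is cut by age.
- The SAE paragraph says "Serious adverse events will be summarized by treatment group and combined over both treatment groups". Its next sentence adds a summary by age group, just before SAE tables 16 and 17.
- Table 18 (AESIs) and table 19 (AEs at 5% or more) have no age split.

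Protocol 13.4.2 summarises treatment-emergent AEs by treatment group, severity and relationship, without age. The subgroup list in protocol 13.4.1 covers efficacy endpoints only.

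On numbers, the SAP's sample-size text says "Approximately 196 subjects (children and adolescents) will be enrolled into the open-label Stabilization" Period, and that "approximately 40 adult subjects are also expected to be enrolled".

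**The concern.** The objective names three age groups, but the planned AE output does not separate them. Someone who follows the table list exactly would obtain preferred-term incidence for non-serious AEs and AESIs in one all-ages Safety Set. That figure is dominated by children and adolescents, so it says little about adults. It also does not match the primary efficacy population, which is 6 to <18 years: benefit would be reported for minors and non-serious harm for minors and adults together.

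The existing splits do not stand in for age. Adolescents and adults share the upper weight bands. Initial daily dose takes only two values, fixed by whether baseline weight is above 44 kg, so it carries less information than weight band. The Extrapyramidal Symptom Rating Scale and the Columbia suicidality scale are given to all ages and summarised by treatment group only (SAP 12.6, 12.7.3), so the pooling also reaches two of the AESI topics.

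**Working it through.** **The plan's own enrolment figure**

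Inputs from SAP 4.3 and the text on total number of subjects: 98 minors randomised, 49 per group; relapse in 65% on placebo and 34% on ecopipam; 50% open-label response.
- Expected relapses: 49 × 0.65 + 49 × 0.34 = 48.5, against the planned 49.
- Minors enrolled: 98 / 0.50 = 196, as stated.

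**Make-up of the Safety Set**

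- Planned total: 196 + 40 = 236.
- Paediatric share: 196/236 = 83.1%. Adult share: 40/236 = 16.9%.
- Forty adults is an expectation, not a quota. For an assumed range of 20 to 60 adults, the paediatric share is 196/216 = 90.7% to 196/256 = 76.6%.

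**Effect on table 19, with no outside rates needed**

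The 5% cut-off is applied here to the whole Safety Set; the SAP does not state the denominator. For an AE that occurs only in adults:
- Required adult rate = 0.05 × 236 / 40 = 29.5%.
- With 20 adults: 0.05 × 216 / 20 = 54%. With 60 adults: 0.05 × 256 / 60 = 21.3%.
- If minors have the AE at an assumed 2%: (0.05 × 236 − 0.02 × 196) / 40 = 19.7%.

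**Illustration with the protocol's earlier rates**

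Protocol 5.2.2 gives AE rates for the adult study PSY301 (18 subjects, open-label) and for the paediatric trial EBS-101-CL-001. Pooled rate = (196 × paediatric rate + 40 × adult rate) / 236.

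| AE | Paediatric % | Adult % | Pooled % | Adult / pooled | Pooled / paediatric |
|---|---|---|---|---|---|
| Headache | 15.8 | 22 | 16.9 | 1.3 | 1.1 |
| Somnolence | 7.9 | 28 | 11.3 | 2.5 | 1.4 |
| Insomnia | 9.2 | 33 | 13.2 | 2.5 | 1.4 |
| Anxiety | 5.3 | 22 | 8.1 | 2.7 | 1.5 |
| Fatigue | 7.9 | 33 | 12.2 | 2.7 | 1.5 |

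**How firm that illustration is**

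- 33% of 18 is 6 subjects (exact 95% CI 13% to 59%); 22% of 18 is 4 (6% to 48%).
- With the paediatric rates held fixed, the understatement runs from 1.3- to 3.3-fold for insomnia and from 1.2- to 3.8-fold for anxiety.
- The paediatric open-label study EBS-101-OL-001 reports anxiety at 9.1%. The pool is then (196 × 9.1 + 40 × 22) / 236 = 11.3%, and the ratio 22 / 11.3 = 1.9.

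**What adult tables could show**

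- Open-label period, about 40 adults: an observed 13/40 has an exact 95% CI of 19% to 49%.
- Randomised withdrawal (R/WD) period: 40 × 0.50 / 2 = 10 adults per arm. The 50% response is borrowed from the paediatric assumption; the documents give none for adults.

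**The case against.** The strongest reply is that much of the safety plan is already age-specific.
- Depression, anxiety, ADHD and OCD are measured on separate paediatric and adult instruments, each with its own summary (SAP 12 and 12.7).
- ECG outlier criteria are set separately for adults, adolescents and children (SAP 12.4).
- SAEs are summarised by age group (SAP 12.1).
- SAP 8.6 applies the age groups to disposition. SAP 9.1 includes reasons for premature discontinuation in both periods, and protocol 7.5 lists AEs as one such reason. Counts of discontinuations for AEs by age are therefore planned.
- Exposure by age is planned, so denominators exist, and individual data are listed.

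All of this stands, and it narrows the gap to AE and AESI incidence by preferred term. A reader might infer that the adult part of the safety objective cannot be answered. The documents do not support that.

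The reply also has force on size. A reader might take the dilution to be 2.5- to 2.7-fold. That range holds only for four selected events. Headache, reported in the same two studies, gives 1.3-fold, and the adult rates come from 18 subjects in a study of different design.

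Two further arguments carry less weight. The objective can be read as simply naming who was enrolled, but it lists the three groups with age limits, and reporting them only together answers it weakly. The age sentence in the SAE paragraph may have been meant for all AEs; as written its subject is SAEs, so that intention would also need an edit.

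Finally, these are descriptive tables with no test and no alpha, and they can be run later from the locked data. That is correct, and it limits the severity.

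**Conclusion.** The point holds in a limited form. No table planned in the SAP gives the incidence of non-serious AEs or of AESIs by age group, although safety in three age groups is a secondary objective. Those incidences would be reported only for a pool planned as about 83% paediatric (91% to 77% if adults number 20 to 60).

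The firmest measure of the effect is the table 19 threshold. An AE confined to adults would need an adult rate of about 29.5% to be listed, given 40 adults and the whole Safety Set as denominator. The 1.3- to 2.7-fold understatement of adult rates is illustrative only, because it rests on small earlier studies of different design.

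No efficacy conclusion, error rate or sample size is affected. This is a worthwhile improvement to reporting, not a flaw that puts the trial's conclusions at risk.

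**What to change.** Either add AEs to the items split by age in SAP 8.6, or add age columns (6 to <12, 12 to <18, 6 to <18 combined, and 18 and over) to at least three tables in SAP 12.1: the overall AE summary (table 1), AEs by system organ class and preferred term (table 2), and AESIs (table 18). Produce them for the open-label period and, descriptively, for the R/WD period by arm. If the age sentence in the SAE paragraph was meant to cover all AEs, say so there.

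The cost is SAP wording and repeat runs of existing tables, with no change to trial conduct. The downside is more output and imprecise adult estimates: about 40 adults in the open-label period, and about 10 per arm in the R/WD period if adults also respond at 50%. The tables should be labelled descriptive.
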